3.3 Exploratory objectives

4 To explore the kidney and vascular endothelial function assessed by a panel of molecular markers over the observation period. Study design

Randomized, single center parallel-group, open-label study.

Pilot study with exploratory objectives.

Eligibility: All primary or retransplant recipients of deceased donor or living donor grafts with negative crossmatch who are felt to have good expectations for renal function recovery after surgery will be offered entry into the study.

Treatment scheme is as described above, with Solumedrol 500 mg IV in OR as induction, then 5 doses of Thymoglobulin starting morning of POD 1 at 1.25 mg/dose (rounded to nearest 25 mg) with rapid steroid taper over five doses. The mTOR inhibitor drug will be started on POD 0 and Neoral introduced as renal function recovers, usually starting on POD 2.

Measurement/Assessments: as described above, graft and patient survival per standard definitions, clinically indicated biopsies for determination of acute cellular or antibody mediated rejection, renal function as estimated from serum Cr based on MDRD, clinic visits for wound assessment, standard of care labs for renal function, bone marrow function (WBC and platelet count), liver function, lipid panel, donor specific antibody determination during any significant increase in serum Cr, drug levels routinely monitored for need of number of dose adjustments and compliance, Emergency Room and hospitalizations, as well as unscheduled clinic and other physician visits. For the pilot study, we would perform scheduled CMV, EBV and serum BK PCRs monthly for the first year, then quarterly or with any viral symptoms.

A subset of patients will have coded plasma samples sent to clinical research and development at the University of Colorado. These biomarker samples will be used to assess vascular endothelial dysfunction and inflammation markers as well as kidney dysfunction markers.

Plasma samples are collected and stored at The Ohio State University Wexner Medical Center tissue typing lab per standard of care.

5 Population

The patient population will be all adults (18-75 years of age) who receive a living donor or deceased donor renal transplant as a first or subsequent renal transplant procedure only (no extra-renal organ transplant recipients). We will invite any patient who would normally be considered for our current Sirolimus®/ Neoral® protocol with Thymoglobulin® and steroid induction to consent for this pilot study and then undergo randomization post-operatively if the transplant surgeon anticipates normal early graft function. If there were significant concerns for prolonged graft dysfunction, then the patients will not be invited into the pilot study. Invited patients would include anyone currently not on steroids prior to transplantation, and those with no known intolerance to any of the drugs mentioned. Patients must also be willing to perform the expectations of the study protocol reliably.

This will be a single center pilot study performed at The Ohio State University Comprehensive Transplant Center. Our center performs approximately 100 to 110 living donor and 90 to 100 deceased donor renal transplants per year. If we assume that at least 150 patients per year qualify for the study, then a conservative estimate of 75 enrolled patients a year is possible. We would propose to enroll a total of 60 patients over 12 months, and then follow these patients for a complete 3 years. We will randomize 2:1 Zortress to Sirolimus using a random number generator.

5.1 Inclusion criteria

Patients eligible for inclusion in this study have to fulfill all of the following criteria at the time of enrollment:

1. Patients must give written informed consent before any assessment is performed.
2. Primary renal transplant recipients between ages 18 and 75 years of age.
3. Females capable of becoming pregnant must have a negative pregnancy test prior to transplantation and practice an effective form of birth control for the duration of the study and 12 weeks after discontinuation of the study drug if applicable.

5.2 Exclusion criteria

- Exclusion Criteria at the time of enrollment:
 - Total cholesterol > 300 mg/dl or triglycerides > 400 mg/dl despite lipid lowering therapy
 - Pre-existing bone marrow suppression (WBC < 3000, platelets < 100,000)
 - Positive crossmatch or ABO incompatible

- Pregnant or nursing (lactating) women, where pregnancy is defined as the state of a female after conception and until the termination of gestation, confirmed by a positive serum human chorionic gonadotrophin laboratory test (>5 mIU/mL)
- Women of child-bearing potential, defined as all women physiologically capable of becoming pregnant, including women whose career, lifestyle, or sexual orientation precludes intercourse with a male partner and women whose partners have been sterilized by vasectomy or other means, UNLESS they are using two birth control methods. The two methods can be a double barrier method or a barrier method plus a hormonal method.
 - Adequate barrier methods of contraception include: diaphragm, condom (by the partner), intrauterine device (copper or hormonal), sponge or spermicide. Hormonal contraceptives include any marketed contraceptive agent that includes an estrogen and/or a progestational agent.
 - Reliable contraception should be maintained throughout the study and for 12 weeks after study drug discontinuation.
 - Women are considered post-menopausal and not of child bearing potential if they have had 12 months of natural (spontaneous) amenorrhea with an appropriate clinical profile (e.g. age appropriate, history of vasomotor symptoms) or six months of spontaneous amenorrhea with serum FSH levels > 40 mIU/mL and estradiol < 20 pg/mL] or have had surgical bilateral oophorectomy (with or without hysterectomy) at least six weeks ago. In the case of oophorectomy alone, only when the reproductive status of the woman has been confirmed by follow up hormone level assessment is she considered not of child bearing potential.
- Active infection (HBV, HIV)
- Malignancy (except for adequately treated squamous or basal cell skin carcinoma) unless patient has written clearance from an Oncologist or if patient has had no malignancy for at least 2 years prior to the transplant
- Allergy or intolerance to sirolimus, everolimus, cyclosporine, or ATG

6 Treatment

6.1 Investigational and control drugs

Zortress will be started on POD #0 and initially dosed at 0.75 mg BID (12 hours apart) dosed simultaneously with Neoral and the dose adjusted thereafter to achieve a target trough serum level between 3 ng/ml and 8 ng/ml. Sirolimus will be dosed per our standard approach, specifically started on POD #0 at 5 mg/d, decreasing to 3 mg/d on POD #2, and adjusted thereafter to achieve a target trough serum level of 10 to 18 ng/ml by Architect assay, or 8 to 12 by LC-MS methodology.

6.2 Treatment arms

Patients will be assigned to one of the following “n” treatment arms in a ratio of 2:1; Zortress or Sirolimus started on POD 0, with Solumedrol 500 mg IV in OR as induction, then 5 doses of Thymoglobulin starting morning of POD 1 at 1.25 mg/dose (rounded to nearest 25 mg) with rapid steroid taper over five doses. Neoral will be introduced as renal function recovers, usually starting on POD 2. We will enroll a total of 60 patients.

- Zortress and Neoral, with Thymoglobulin induction and perioperative steroids
- Rapamycin and Neoral, with Thymoglobulin induction and perioperative steroids

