Investigational and reference therapy: Zortress® bid for goal levels of 3 to 8 ng/ml by approved testing methods; Rapamune® goal levels of 10 to 18 ng/ml by Architect assay, or 8 to 12 by LC-MS methodology; Neoral® goal levels of 800 to 1000 ng/ml by immunoassay until 3 months Post-transplant, 600-800 ng/ml 3-6 months post-transplant, 400-600 ng/ml 6-12 months post-transplant, and 400 ng/ml > 12 months post-transplant. Induction agents: Thymoglobulin 1.25 mg/kg for 4 to 5 doses adjusted for white blood count and platelet count, as well as appropriate levels of the two maintenance immunosuppressive agents, and steroids given as methylprednisolone IV for two doses, then oral prednisone at: 500 mg, 200 mg, 125 mg, 50 mg, and 25 mg.

Study design: Randomized, single center parallel-group, open-label study.

Pilot study with exploratory objectives.

Eligibility: All primary or retransplant recipients of deceased donor or living donor grafts with negative crossmatch who are felt to have good expectations for renal function recovery after surgery will be offered entry into the study.

Treatment scheme is as described above, with Solumedrol 500 mg IV in OR as induction, then 5 doses of Thymoglobulin starting morning of POD 1 at 1.25 mg/dose (rounded to nearest 25 mg) with

rapid steroid taper over five doses. The mTOR inhibitor drug will be started on POD 0 and Neoral introduced as renal function recovers, usually starting on POD 2.

Measurement/Assessments: as described above, graft and patient survival per standard definitions, clinically indicated biopsies for determination of acute cellular or antibody mediated rejection, renal function as estimated from serum Cr based on MDRD, clinic visits for wound assessment, standard of care labs for renal function, bone marrow function (WBC and platelet count), liver function, lipid panel, donor specific antibody determination during any significant increase in serum Cr, drug levels routinely monitored for need of number of dose adjustments and compliance, Emergency Room and hospitalizations, as well as unscheduled clinic and other physician visits. For the pilot study, we would perform scheduled CMV, EBV and serum BK PCRs monthly for the first year, then quarterly or with any viral symptoms.

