Potential study participants will be approached for consent immediately prior to transplantation by the transplant surgeon or appointed representative if they meet the inclusion criteria above and do not fit the exclusion criteria above. If the transplant candidate agrees to participate he/she will be categorized as a living or deceased donor kidney recipient category and as primary or subsequent kidney transplant recipient. The candidate will then be randomized, in a 2:1 fashion, to either the Zortress or Rapamune study arm. Following transplantation all recipients will receive daily Thymoglobulin doses of 1.25 mg/kg starting on POD #1 for 4 to 5 doses adjusted for white blood count and platelet count. All recipients will be administered steroids as methylprednisolone IV for two doses, then oral prednisone at: 500 mg, 200 mg, 125 mg, 50 mg, and 25 mg and will receive delayed Neoral® on POD #2-3 dosed to achieve serum levels of 800 to 1000 ng/ml by immunoassay until 3 months post-transplant, 600-800 ng/ml 3-6 months post-transplant, 400-600 ng/ml 6-12 months post-transplant, and 400 ng/ml > 12 months post-transplant. Zortress® will be started on POD #0 for Zortress study arm recipients, administered bid and dosed to achieve target levels of 3 to 8 ng/ml by approved testing methods; Rapamune® study arm recipients will receive Rapamune once daily, dosed to achieve target levels of 10 to 18 ng/ml by Architect assay, or 8 to 12 by LC-MS methodology. Neoral and Rapamune/Zortress levels will be monitored twice weekly for the first 3 months, once weekly for months 3-6, every other week months 6-12, and monthly thereafter. This pilot study is estimated to take one year for enrollment and three years from the date of last patient enrollment for completion of last patient visit, then several months for completion of paper work. This will be about 4.5 to 5 years.

Efficacy assessments:

- Incidence of graft loss in the first post-transplant year
- Incidence of patient death in the first post-transplant year
- Incidence of acute rejection at 1 year post-transplant

Other assessments:

- Incidence of non-death censored graft loss at 6 months, 2 and 3 years after transplantation
- Number and grade of acute rejection episodes at 6 months, 1, 2, and 3 years after transplantation
- Tolerability of Zortress at 1 year post-transplant
- Estimated GFR at 6 months, 1, 2, and 3 years after transplantation
- Incidence of CMV, EBV and BK infections 1 year after transplantation

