Two prospective randomized trials (A2306 and A2307) have demonstrated that everolimus combined with steroids and low dose Neoral with (A2307) or without (A2306) basiliximab induction result in excellent 1 year outcomes (1). In 2002 we adopted an immunosuppressive regimen using Rapamune and reduced dose Neoral without steroids using induction therapy with Thymoglobulin. Since employing this regimen our acute rejection rate within the first year post-transplant has been between 7% and 10% for any given calendar year. However, many patients need to have their Rapamune discontinued due to drug related side effects or compliance difficulties related to the noon dosing (when most other medications are taken at 8 am and 4 pm). We feel strongly that use of an alternative drug to Rapamune in such cases is necessary. Use of Zortress in this setting would be ideal, however, no data currently exists concerning the use of Zortress with Neoral in a steroid free maintenance immunosuppression regimen following Thymoglobulin induction. Thus we propose this pilot study primarily to verify Zortress efficacy using our established immunosuppressive protocol. Secondarily we are interested in characterizing the Zortress drug related side effect profile to enable us in the future to exploit any favorable differences between Zortress and Rapamune.

2 Purpose and rationale

Our center's renal transplant immunosuppression protocol has consisted of Thymoglobulin and steroid induction for 5 doses only, with early initiation of Rapamune® (Sirolimus) and then Neoral for nearly a decade now. We do observe a significant amount of adverse events in our patient population, with many of these potentially related to the Sirolimus. The combination of "half-dose" cyclosporine (early C2 levels around 800 to 1000 ng/ml) allows us to minimize calcineurin inhibitor toxicity and its combination with the mTOR drug Sirolimus provides excellent protection against acute rejection in our renal transplant recipients. Our earlier experience with Everolimus and the recent publications describing renal recipients' outcomes with this drug, suggest to us that our patients may do better on Everolimus than Sirolimus (1,2). For our center, this pilot study would be very straightforward as the only difference in medication from our current well established protocol would be the randomization to either Rapamune®, our current standard of care, or Zortress®, the study drug.

3 Objectives

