7.1 Table 7-1

Assessment schedule:

Visit number	1 Screening/ Baseline	2	3	4	5	6	7	8	9	10	11	12	13	14	15	16	17	18
Time of Visit		Day 0	Day 1	Day 2	Day 3	Day 4	Day 5 ¹	Day 6 ¹	Day 7 ¹	Wk 2	Mo 1	Mo 2	Mo 3	Mo 6	Mo 12	Mo 18	Mo 24	Mo 36
Inclusion/Exclusion criteria	X																	
Informed consent	X																	
Physical examination	X	X	X	X	X	X	X	X	X	X	X	X	X	X	X	X	X	X
Demographics	X																	
Medical History	X																	
Pregnancy Test ²	X																	
Vital signs	X	X	X	X	X	X	X	X	X	X	X	X	X	X	X	X	X	X
Hematology		X		X				X	X	X	X	X	X	X	X	X	X	X
Chemistry		X			X			X	X	X	X	X	X	X	X	X	X	X
Lipid panel	X									X	X	X	X	X	X	X	X	X
24 hour urine												X	X	X	X	X	X	X
Alloscreen	X															X		
Flow Crossmatch	X															X		
HGB A1C																X		X
Kidney Biopsy	X															X		
Adverse events		X	X	X	X	X	X	X	X	X	X	X	X	X	X	X	X	X
Cyclosporine level ³				X				X	X	X	X	X	X	X	X	X	X	X
Everolimus level ³					X			X	X	X	X	X	X	X	X	X	X	X
Optional sub study: Plasma for Biomarkers ⁴	X				X			X	X	X	X	X	X	X	X	X	X	X

Legend:

- 1: If still inpatient
- 2: Females capable of childbearing
- 3: Cyclosporine and Zortress levels are monitored twice weekly for 0-3 months post-transplant, every two weeks for 3-12 months post-transplant, and monthly greater than 1 year post-transplant.
- 4: Plasma for biomarkers will be assessed at the University of Colorado in a subset of patients using existing plasma samples.

Patients will be followed as per the standard of care at this transplant center (The Ohio State University Medical Center, Division of Transplantation). Additional study procedures include a protocol biopsy at month 12 and some additional laboratory work at screening/baseline and at months 6, 12, 24, and 36.

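### The Thymoglobulin induction dose is a fixed 1.25 mg per dose in some places and 1.25 mg per kg in others, and nothing in the protocol says which governs

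*Combined protocol and SAP*

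**What the plan says.** Two descriptions of Thymoglobulin induction stand in the combined protocol and SAP.

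**Fixed-amount wording.** Section 6.2, Treatment arms, specifies Solumedrol in the operating room, "then 5 doses of Thymoglobulin starting morning of POD 1 at 1.25 mg/dose (rounded to nearest 25 mg"). The same clause, "5 doses of Thymoglobulin starting morning of POD 1 at 1.25 mg/dose (rounded to nearest 25 mg"), appears in the synopsis under Study design and again in Section 4. It gives no weight basis and no condition for changing the dose or the number of doses.

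**Weight-based wording.** The synopsis paragraph on investigational and reference therapy has "Thymoglobulin 1.25 mg/kg for 4 to 5 doses adjusted for white blood count and platelet count", and continues "as well as appropriate levels of the two maintenance immunosuppressive agents". A later synopsis paragraph, on consent, randomization and treatment, has "daily Thymoglobulin doses of 1.25 mg/kg starting on POD #1 for 4 to 5 doses adjusted for white blood count and platelet count". It leaves out the condition on maintenance-drug levels. Neither paragraph has a rounding rule.

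**Cross-references and current practice.** The treatment-scheme sentence in Section 4, repeated in the synopsis, opens "Treatment scheme is as described above, with Solumedrol 500 mg IV in OR as induction, then 5 doses of Thymoglobulin". Section 2 and the matching synopsis paragraph describe the center's existing regimen as "Thymoglobulin and steroid induction for 5 doses only", without an amount.

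**The concern.** A dose in mg and a dose in mg per kg are different instructions. Thymoglobulin induction is given to every patient in both arms, so the figure applies to all 60 planned patients. Someone working from Section 6.2 and someone working from the synopsis hold different written orders on the unit. The texts also differ on whether to round, whether fewer than five doses may be given, and on what grounds.

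What is at stake is patient safety, consistent delivery, and the ability to judge adherence to the background regimen or reproduce it. Section 1 says the trial is meant to verify Zortress within the center's established protocol, so that protocol should be stated once and consistently. The treatment comparison is not at stake: induction is common to both arms, and Section 10 plans no analysis of Thymoglobulin exposure.

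**Working it through.** **1. Side by side.**

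| Location | Unit | Rounding | Doses | Adjustment |
|---|---|---|---|---|
| Synopsis, therapy paragraph | 1.25 mg/kg | none stated | 4 to 5 | white cells, platelets, maintenance-drug levels |
| Synopsis, consent and treatment paragraph | 1.25 mg/kg | none stated | 4 to 5 | white cells, platelets |
| Synopsis, Study design | 1.25 mg per dose | multiple of 25 mg | 5 | none stated |
| Section 4 | 1.25 mg per dose | multiple of 25 mg | 5 | none stated |
| Section 6.2 | 1.25 mg per dose | multiple of 25 mg | 5 | none stated |

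**2. Does any text settle it?**
- In the synopsis, the reference back to a scheme described above follows the weight-based paragraph, yet the same sentence then states the fixed amount.
- In Section 4, Sections 1 to 3 give no Thymoglobulin amount. The reference can therefore reach only the synopsis, which holds both wordings.
- Section 6.2 has no cross-reference for the dose.
- Section 6.1 gives doses only for Zortress and sirolimus. Section 6.5.4 permits adjustments only for those two drugs. The body therefore contains no weight-based Thymoglobulin dose and no blood-count adjustment for it.

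**3. The fixed amount against its own rounding rule.** 1.25 / 25 = 0.05, and the nearest whole number is 0, so the rounded dose is 0 × 25 = 0 mg. The smallest amount that can round to 25 mg is 25 / 2 = 12.5 mg, and 12.5 / 1.25 = 10. The stated amount is ten-fold below that threshold. This step needs no outside figure.

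**4. Size of the gap between the wordings, before rounding.** Per dose the ratio is (1.25 × weight in kg) / 1.25 = weight in kg. The fixed-amount course is 5 × 1.25 = 6.25 mg. The documents give no body weights, so the weights below are assumptions.

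| Assumed weight | mg/kg wording, per dose | Course, 4 doses | Course, 5 doses | Course ratio to 6.25 mg |
|---|---|---|---|---|
| 60 kg | 75 mg | 300 mg | 375 mg | 48 to 60 |
| 70 kg | 87.5 mg | 350 mg | 437.5 mg | 56 to 70 |
| 80 kg | 100 mg | 400 mg | 500 mg | 64 to 80 |
| 100 kg | 125 mg | 500 mg | 625 mg | 80 to 100 |

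Over 60 to 100 kg the gap is 60- to 100-fold per dose and 48- to 100-fold over the course.

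**5. A separate, lesser inconsistency.** Note 3 to Table 7-1 sets drug levels "every two weeks for 3-12 months post-transplant", while the synopsis and Section 7.4 have weekly levels in months 3 to 6. Taking three months as about 13 weeks, that is about 13 samples against 13 / 2 = 6.5, so 6 or 7. It concerns other drugs and adds nothing to the severity of the dose conflict.

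**The case against.** The best case on the other side has four parts.

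- **Only the unit truly conflicts.** A rounding rule is compatible with a weight-based dose, five lies within four to five, and an adjustment condition given in one place and omitted in another is not denied there. This largely stands: the unit is the core of the point and the dose count is the mildest part. Even so, the fixed-amount wording gives no ground for fewer than five doses, and the two weight-based paragraphs differ on the adjustment condition.
- **The fold-differences do not describe a likely exposure.** An instruction that rounds to 0 mg would be queried, not delivered, and the weights are assumed. This stands as a limit. The ratios measure how far apart the texts are and do not predict what patients would receive.
- **The three fixed-amount statements are near-verbatim repeats, not independent evidence.** True. But they include every Thymoglobulin amount in the protocol body, so they cannot be set aside as a stray line in the synopsis.
- **Practical risk is low.** This is one center using a regimen it has had for nearly a decade; Section 2 says the randomized drug is the only change in medication. That makes a misreading less likely, but it does not make the text agree.

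The absence of any effect on bias, power or alpha is accepted in full.

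**Conclusion.** The concern holds. The synopsis contradicts itself on the unit of the Thymoglobulin dose, Sections 4 and 6.2 carry only the fixed amount, and no text sets precedence. The fixed amount rounds to 0 mg under the protocol's own rule, which needs no assumption. The factor between the wordings, equal to body weight in kg per dose before rounding, is likewise exact; only its numerical range of 60 to 100 rests on assumed weights.

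Because this is a dose in the operative treatment section for all 60 planned patients, it must be corrected. That judgment rests on safety and consistent delivery alone.

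**What to change.** The clinical team must reconcile the two synopsis paragraphs with the weight-based wording, the synopsis study-design paragraph, Section 4 and Section 6.2. All should state the same dose unit, rounding rule, number of doses and adjustment condition. The body should state the dose itself and not lean on a reference to a description elsewhere. Which version is right is a clinical decision on which this review takes no position.

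As a separate and lesser item, reconcile the months 3 to 6 drug-level schedule between note 3 to Table 7-1, the synopsis and Section 7.4.

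The cost is a written amendment through Section 12.1 covering the synopsis, Sections 4 and 6.2, and the passages on the drug-level schedule. Design, sample size and analysis do not change.
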